### 6.7.2 Hopkins Verbal Learning Test (HVLT)

The Hopkins Verbal learning test (HVLT)  assesses verbal list-learning and memory through immediate recall, delayed recall and delayed recognition (Appendix 15). The test is commonly used to detect dementia and cognitive decline among respondents and allows insight into individuals' memory function. This is a widely-used word learning test which consists of three immediate recall trials followed by a delayed recall 20 minutes later. During this gap, other, non-memory-based cognitive tests may be performed. Parallel forms will be used across different assessment points to minimize potential practice effects.

### 6.7.3 Spatial Span (WMS-III)

A subtest of the Wechsler Memory Scale, 3rd edition (WMS-III) . The test assesses a participant's visual short term memory capacity. The examiner touches an increasingly long sequence of blocks (mounted on a board – see Figure 3) at 1 second intervals, which the participant then repeats. The trial ceases when the participant fails to correctly duplicate the sequence twice at the same length. The second trial involves the participant repeating the reverse sequence of the sequence demonstrated by the examiner. This backward span trial ceases when the participant fails to correctly duplicate the sequence twice at the same length (Appendix 16).

Both trials commence with a 2 block sequence, and two sequences are presented at each sequence length before increasing sequentially to the next sequence length.

**Figure 3: WMS-III Spatial Span board**

#### **6.7.4 Digit Symbol Coding test (WAIS-III)**

This subtest of the Wechsler Adult Intelligence Scale – 3rd edition (WAIS-III)  requires participants to correctly copy symbols that represent numbers and assesses visuomotor information processing speed and attention. Participants complete as many items as they can within a 120 second time limit (Appendix 19).

#### **6.7.5 Trail Making Test (TMT)**

A “join-the-dots” paper and pencil test consisting of two trials . The first trial requires participants to connect a series of numbers from 1 to 25 in numerical order as fast as possible. The second trial requires participants to connect a series of letters (A to L) concurrently with a series of numbers (1-13), such that the connections made are number-letter-number-letter, and so on, in alphabetical and numerical order (Appendix 17). Time taken to complete each trial and number of errors made are recorded

#### **6.7.6 Stroop Test (24 item Victoria Version)**

The 24-item Victoria version of the Stroop test requires subjects to name the ink colour of the print in three separate trials . The first trial requires participants to name the ink colour of clusters of X’s. The second trial requires subjects to name the ink colour of simple nouns (e.g., car). The third trial requires subjects to name the ink colour of colour words (e.g., red), subjects must not name the word, but the colour of the ink in which the word is printed. The complexity on this trial is that the ink colour does not match the word, for example the word “red” might be printed in blue ink and the participant is required to say “blue” not “red”. Time taken to complete each trial and the number of errors made are recorded (Appendix 18).

## 6.8 Psychological assessment

### 6.8.1 Hospital Anxiety and Depression Scale (HADS)

The HADS [7] is a self-report 14 item scale assessing symptoms of depression (7 items) and anxiety (7 items) experienced in the **preceding 7 days**. Responses are given on a 4-item scale, relating to frequency or intensity of symptoms experienced – each item has a score of 0-3 (Appendix 20).

Anxiety scale and Depression scale are scored separately, each scale has a range of 0-21.

For both Anxiety and Depression scales, the following cutoff values apply:

Score	Interpretation
0 – 7	Normal
8 – 10	Mild symptoms
11 – 14	Moderate symptoms
15 – 21	Severe symptoms

## 6.9 Social functioning

### 6.9.1 Lubben Social Network Scale, Short Form (LSNS-R)

The LSNS-R scale is a 12-item questionnaire on which participants respond on a 6 item Likert scale . Of the 12 questions, 6 relate to familial relationships and 6 relate to friendships. There are no reverse scored items (Appendix 21).

LSNS-R Total score is the sum of scores across the 12 items, with subscores for family and friendships being the sum of scores for the 6 items in each. Scores range from 0-60 for LSNS-R Total Score, and from 0-30 for each of the Family and Friendships subscores.

### 6.9.2 UCLA Loneliness Scale

The UCLA Loneliness scale is a 20-item questionnaire on which participants respond on a 4-point Likert scale regarding how frequently they experience feelings of social isolation and loneliness . Of the 20 items, 9 items are reverse scored (i.e. a score of 1 is counted as 4, 2 as 3, etc.). Total score is the sum of scores of the 20 items, following reverse scoring of the 9 reversed items. Total score range is 40-80 (Appendix 22).

## 6.10 Nutrition

### 6.10.1 BMI

The Body Mass Index (BMI) for each participant will be calculated from weight and height data collected at each assessment phase using the following formula:

$$\text{BMI} = [\text{height(m)} / \text{weight (kg)}] / [\text{height(m)}]$$

### 6.10.2 Self-MNA

The Self Mini Nutritional Assessment (Self-MNA)  is a brief questionnaire assessing the nutritional status of adults aged 65 years and older (Appendix 23). The Self-MNA is produced and licensed by Nestle Nutrition Institute, with permission to use this scale in the my-AHA project having been received.

The Self-MNA comprises:

1. 5 items relating to food intake, weight change, mobility, illness, dementia/depression
2. Height and weight measures
3. Circumference measurement of the left calf

Preferably, the scale is investigator administered to ensure consistency of measurement of physical data.

## 6.11 Technology use

### 6.11.1 Computer Literacy Scale (CLS)

The CLS is a brief screening test to assess an individual's level of familiarity with computer based interfaces.

The CLS comprises 2 parts:

- Part 1 – captures basic demographic information and items relating to experience with computers
- Part 2 – assesses a participant's familiarity with the meaning of various icons used by computer based systems as well as the meaning of basic menu options for computer programs.

The CLS will be administered only at baseline assessment.

### 6.11.2 Evaluation of Usability Scale (SUS)

The SUS is a brief 10 item scale assessing a participant's experience with the usability of the My-AHA platform. The participant responds to each of the 10 items on a 5 point scale from "strongly disagree" to "strongly agree"

The SUS will be administered at a single assessment point (12 months) in the RCT protocol.

### 6.11.3 DART Questionnaire

The DART questionnaire surveys the participant's responses to the use of application in the health care sector and their experiences in using the My-AHA application.

- The survey comprises 3 parts:
- Part 1 - collects basic demographic information and responses to the value of the My-AHA application
- Part 2 – comprises 19 items in which the participant rates the level of importance of different features of smartphone or tablet applications in the health care sectors
- Part 3 – comprised the same 19 items repeated, but the participant is asked to respond with reference specifically to the My-AHA application.

### 6.11.4 User Experience Questionnaire (UEQ)

The UEQ is a 26 item scale assessing the participant's description of the attributes of the My-AHA application.

Participants are presented with a series of 26 paired (and opposing) attributes, to which they indicate their level of response on a 7 point scale.

The UEQ will be administered at a single assessment point (18 months) at the completion of the RCT.

## 7 My-AHA Interventions

The intervention in this study is defined as the My-AHA platform. Participants randomized into the intervention arm will have access to the full My-AHA intervention platform (see also Section 8 My-AHA User Platform interface). Participants in the control group will not have access to the intervention package (no treatment control). All participants recruited into the study have no active disease state being treated. All participants meet study criteria for pre-frail status, a non-clinical disease state.

The protocol in the intervention arm is designed to prevent deterioration from a non-clinical state (pre-frail) into the disease state (frail).

The no-intervention control arm will not receive any element of the My-AHA intervention, a no-intervention non-disease control group. Participants in both study arms undergo formal assessment of clinical frailty status at 4 timepoints (baseline, 6 mo, 12 mo, 18mo). **Development of clinical frailty is considered an adverse endpoint for the participant in this study.**

Where a control group participant displays evidence of clinical decline at 6 or 12mo assessment points (defined as meeting clinical criteria for frailty) they will be offered access to the My-AHA intervention suite. We cannot estimate or predict what proportion of the control participants may develop frailty during the 18 month trial as there is no published data on incidence, age-dependent prevalence, or on average rate of decline into frailty from pre-frail states.

Participants randomly allocated to the intervention group will be provided with access to tailored intervention packages. Intervention packages will target domains of pre-frailty (e.g. physical, social, cognitive, nutrition) identified at baseline assessment for each participant. The intervention packages will be revised following each assessment point to accommodate for changes in domain specific areas of pre-frailty.

**IMPORTANT NOTE:** For participants in the control group access to interventions will not be provided – this is a no-treatment control group. **The exception is when a control participant is found to meet clinical criteria for physical frailty at any of the post-baseline assessment points (6 month or 12 month). If progression to physical frailty is detected in a control group participant, that participant will be provided with immediate fully supported access to the physical intervention package to meet ethical obligations to the participant.**

## 7.1 Physical Interventions

As the key physical markers of frailty are: weight loss, physical weakness, reduced endurance and energy, motor slowing, and reduced physical activity; interventions have been selected to target these key physical indicators of frailty. With falls being the most likely consequence of increasing physical frailty, prevention of falls through balance training to enhance gait pattern and postural control is a key approach to be employed in the My-AHA project. In addition to fall prevention, endurance training will also be provided to increase physical activity levels, improve cardiovascular-fitness and therefore increase energy levels and endurance capacity.

The multicomponent physical intervention deployed in the My-AHA project involve activities that combine strength, balance and endurance training over an extended duration ( $\geq 5$  months), with high frequency repetition (performed three times per week) for 30–45 minutes per session. Such physical interventions have been found to result in superior outcomes compared to other exercise programs and that exercise interventions combining strength, endurance and balance training display the greatest reduction in falls rate and improvement in gait, balance, and strength performance in physically frail older adults.

For the strength and balance domains, the OTAGO (OEP) home-based exercise program, the Fitness and Mobility Exercise program FAME, and endurance training will be applied. Guidelines for endurance training will be provided based on the participants' maximum heart rate (HRmax), with participants being able to choose the type of endurance activity from a range of options (e.g., walking, Nordic walking, bicycling, stationary bicycling, treadmill).

### 7.1.1 *Otago home-based exercise program (OEP)*

The OEP will be deployed as a home-based exercise programme used by older adults in their own homes without expert's supervision. Prior to commencing the OEP program each participant will have a home visit from an exercise instructor who will prescribe an individually tailored set of exercises according to the participant's clinical history and fitness level. The instructor will also provide each participant with detailed instructions regarding the correct implementation of each exercise. Participants will be provided with a booklet listing the exercises including short description and repetitions for each set as well as adjustable ankle cuff weights, which must be easy to take on and off. For participants, unable to exercise from a standing position, a chair-based exercise programme will be provided resistance-based training using ankle weights being replaced with resistance-bands.

Participants will undertake the OEP program one session per week, as each participant will engage in one additional group-based exercise session that targets the same domains as in the OEP. In addition, the OEP advice of undertaking a walking activity will be replaced with a recommendation of undertaking some form of endurance training for one additional session per week. This modified OEP program, including group exercise and endurance training, will result in a total of 3 hours of physical training per week.

### 7.1.2 *Fitness and Mobility Exercise program (FAME)*

FAME is a standardised group-based exercise programme which participants will complete one session per week under the supervision of a physical exercise instructor (appropriately qualified and trained fitness instructors, physical therapists or occupational therapists). Each group session will be undertaken with a ratio of no greater than 1 instructor per 5 participants.

### 7.1.3 Endurance exercise programs

The endurance training exercise programs will be delivered in accordance with the guidelines of the American Heart Association and the American College of Sports Medicine for endurance training for older adults [18] and aims to reach the proposed recommendations of physical activity (150 min/week) by Month 9 of the RCT. The walking part of the OEP will be replaced by an endurance training suggested to be undertaken for one session per week, with the endurance training activity to be selected by each participant to increase compliance (e.g. walking, Nordic walking, bicycling, treadmill or stationary bicycling). Intensity of the endurance training will start at a moderate level the first few months before gradually increasing to vigorous level activity adjusted for the participants' estimated maximum heart rate (HRmax = 220bpm - age). The intensity rate (HRMax) to training duration is specified in Table 7. Participants are able to halt intensity increases if they perceive the level of intensity is too difficult. However, participants will be required to maintain a minimum of 65% of the HRmax for at least 150 Min per week.

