**Table 7: Intensity and duration of endurance training over 18 month RCT as determined by HRMax**

Month	Intensity (%HR max)	Min/session
1-2	50%	30
3-4	55%	35
5-8	60%	40
9-12	65%	40
13-16	65%	45
17-18	70%	45

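### Section 7.1.3's option to halt intensity increases conflicts with its undated minimum of 65% of HRmax for 150 minutes a week, which also does not fit Table 7 or the weekly session count

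*Protocol*

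**What the plan says.** Four statements in Protocol Section 7.1.3 and its table bear on how hard and how long a participant should train.

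- **Schedule.** "The intensity rate (HRMax) to training duration is specified in Table 7". Table 7 gives 50% of HRmax in Months 1-2, 55% in Months 3-4, 60% in Months 5-8, 65% in Months 9-16 and 70% in Months 17-18. Sessions last 30 to 45 minutes.
- **Halt option.** "Participants are able to halt intensity increases if they perceive the level of intensity is too difficult". No month or lower limit is attached to this sentence.
- **Minimum.** The next sentence begins with However and says that "participants will be required to maintain a minimum of 65% of the HRmax for at least 150 Min per week". It names no start month.
- **Volume and frequency.** The programme "aims to reach the proposed recommendations of physical activity (150 min/week) by Month 9 of the RCT", and the section describes "endurance training suggested to be undertaken for one session per week".

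Maximum heart rate is estimated as "HRmax = 220bpm - age".

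**The concern.** A participant, instructor or site that applies these sentences together cannot satisfy all of them. The table asks for an intensity below the stated minimum in the early months. The halt option lets a participant stay at a level that the next sentence rules out.

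Two things are at stake.

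- **The delivered intervention.** It depends on which sentence is followed. The participants are pre-frail adults aged 60 and over who choose their own endurance activity. Section 7.1.3 describes no supervision of endurance sessions, whereas the group sessions in Section 7.1.2 are supervised. Such participants need one clear heart-rate instruction, and sites should not have to choose between rules.
- **Review of heart-rate data.** Table 6 lists a heart rate monitor with a calendar and diary for endurance adherence. A recorded heart rate cannot be called compliant or not until a single target is fixed. This affects intensity only. Section 6.3 records complete and incomplete sessions, and that can still be done.

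**Working it through.** No sample-size or test calculation is involved. The check compares each row of Table 7 with the minimum in Section 7.1.3.

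**1. Schedule against the minimum, read literally (no start month).** Shortfall = 65% minus the Table 7 intensity.

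| Months | Table 7 intensity | Shortfall from 65% | Months in period |
|---|---|---|---|
| 1-2 | 50% | 15 points | 2 |
| 3-4 | 55% | 10 points | 2 |
| 5-8 | 60% | 5 points | 4 |
| 9-12 | 65% | none | 4 |
| 13-16 | 65% | none | 4 |
| 17-18 | 70% | none | 2 |

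Months below the minimum: 2 + 2 + 4 = 8 of 18, or 44%.

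**2. Halt option against the minimum.** A halted increase leaves the participant at the previous level.

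| Increase | Level after halting | Literal reading | Minimum from Month 9 only |
|---|---|---|---|
| Month 3, 50% to 55% | 50% | below | allowed until Month 9, then below |
| Month 5, 55% to 60% | 55% | below | allowed until Month 9, then below |
| Month 9, 60% to 65% | 60% | below | below at once |
| Month 17, 65% to 70% | 65% | meets it | meets it |

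On the literal reading, one of the four increases can be declined without breach. On the Month 9 reading, two more can be declined, but only for a time. A participant who had halted at 50% would have to rise by 65 - 50 = 15 points at Month 9, whereas each scheduled step in Table 7 is 5 points.

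**3. The gap in beats per minute (illustration only).** The ages are assumptions, and HRmax = 220 - age. The gap applies to Months 1-8 on the literal reading.

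| Assumed age | HRmax | 65% | 50% / 55% / 60% | Gap |
|---|---|---|---|---|
| 60 | 160 | 104 | 80 / 88 / 96 | 24 / 16 / 8 bpm |
| 70 | 150 | 97.5 | 75 / 82.5 / 90 | 22.5 / 15 / 7.5 bpm |
| 80 | 140 | 91 | 70 / 77 / 84 | 21 / 14 / 7 bpm |

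**4. Weekly minutes.** This step assumes that the 150 minutes refers to endurance training. One session a week gives 30, 35, 40 or 45 minutes, depending on the period, so the total is below 150 in all 18 months. Sessions needed per week: 150/30 = 5.0, 150/35 = 4.29, 150/40 = 3.75 and 150/45 = 3.33.

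**The case against.** The strongest reply is that the minimum was meant to start at Month 9. Its full wording joins 65% to 150 minutes a week. The same section aims to reach 150 minutes by Month 9, which is also when Table 7 first shows 65%. To maintain a level suggests that it has already been reached. On this reading, following Table 7 in Months 1-8 breaches nothing, the figures of 8 months and 7-24 bpm fall away, and halts at Months 3 and 5 are permitted until Month 9.

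This is plausible, and it limits what can be claimed. It does not settle the matter. The text ties Month 9 to the aim for weekly minutes, not to the 65% requirement. The reading also leaves the halt option in conflict with the minimum from Month 9 onward.

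A second reply is that However makes the minimum an express limit on the halt option, and a permission with a limit is not a contradiction. That is fair as grammar. But the limit then removes the option at the Month 9 step, and it says nothing about a participant who is already below 65% because of an earlier, permitted halt.

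A third reply concerns the minutes. The 150 minutes may count all physical activity, and Section 7.1.1 puts total training at 3 hours (180 minutes) a week. On that view the shortfall in minutes is not established, so the point is conditional. It would still be unclear whether the 65% minimum applies to the strength and balance sessions.

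Finally, Table 3 excludes clinically significant cardiovascular disease, respiratory disease and untreated hypertension. The documents do not quantify any harm from the ambiguity, and none is claimed here.

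**Conclusion.** The concern holds as an unresolved conflict between the halt option, the 65% and 150-minute requirement, and Table 7. Its size depends on the unstated start month.

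- **Literal reading:** Table 7 is below the minimum in 8 of 18 months, by 5 to 15 points of HRmax, and only the Month 17 increase can be halted without breach.
- **Month 9 reading:** there is no conflict in Months 1-8. Anyone who has halted at 50-60% is below the minimum from Month 9, and the step from 60% to 65% cannot be declined.
- **Minutes:** if they refer to endurance training, one weekly session gives 30-45 of the 150 minutes in every period, whichever start month applies.

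A reader might infer that everyone who follows Table 7 breaches the protocol for eight months and that the halt option is void before Month 17. The documents do not establish this, because the coincidence of the 150-minute aim and the first 65% row at Month 9 leaves a milder reading open. A reader might also infer that endurance adherence cannot be scored at all. That goes too far, since session completion can still be recorded and only the judgement of heart-rate intensity lacks a fixed target.

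The point is worth correcting but does not undermine the trial. The beats-per-minute figures rest on assumed ages and are illustrative.

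**What to change.** Reconcile the halt sentence, the sentence on 65% and 150 minutes, the session frequency and Table 7 into one rule in Section 7.1.3. The rule should state:

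- from which month, if any, the minimum applies;
- whether it binds a participant who has halted, including one who halted before that month;
- whether the 150 minutes counts endurance training only or all physical activity, and how that fits the number of sessions per week.

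Carry the same rule into the participant guidance and any review of heart-rate data. Which intensity, duration or frequency is right is for the clinical team, and this review proposes none.

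The cost is a short text change in Section 7.1.3, with Table 7 or the session frequency adjusted if the team so decides, and matching participant guidance. No extra data are needed. Under Section 11.1.2 the change needs ethics committee approval before it is implemented.

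### The required 150 minutes a week of endurance exercise is 3.3 to 3.75 times what the protocol's own schedule provides, and its weekly programme totals also disagree

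*Protocol*

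**What the plan says.** Section 7.1.3 contains both a weekly target and a weekly schedule for endurance training.

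- **Target.** The endurance programme "aims to reach the proposed recommendations of physical activity (150 min/week) by Month 9 of the RCT". Later in the same paragraph, "participants will be required to maintain a minimum of 65% of the HRmax for at least 150 Min per week".
- **Frequency.** The walking part of the Otago programme (OEP) is replaced by "endurance training suggested to be undertaken for one session per week". Section 7.1.1 agrees, describing "a recommendation of undertaking some form of endurance training for one additional session per week".
- **Session length and intensity.** Table 7 gives 30 to 40 minutes at 50–60% of HRmax in Months 1–8, 40 minutes at 65% in Months 9–12, 45 minutes at 65% in Months 13–16, and 45 minutes at 70% in Months 17–18.
- **Freedom to stop progressing.** "Participants are able to halt intensity increases if they perceive the level of intensity is too difficult". The 65% and 150-minute requirement follows directly.

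Two statements describe the whole physical programme. Section 7.1 describes the intervention as "performed three times per week) for 30–45 minutes per session". Section 7.1.1 says that the modified OEP, with group exercise and endurance training, "will result in a total of 3 hours of physical training per week". Sections 7.1.1 and 7.1.2 make up that week from one OEP session, one FAME group session and one endurance session.

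**The concern.** The requirement and the schedule cannot both describe the planned endurance component. One session of the length in Table 7 falls far short of 150 minutes, and the protocol schedules no further endurance sessions. The wording is also mismatched: the session is suggested or recommended, while the minutes are required.

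At stake is what participants are asked to do. From Month 9, staff working from the session schedule would prescribe 40–45 minutes of endurance work a week, and staff working from the requirement would prescribe 150. The participants are pre-frail people aged 60 and over, and part of the programme is done at home without expert supervision. Control participants who become physically frail are given the same physical package (Section 7).

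The ambiguity carries over to describing the dose delivered. Section 6.3 says the platform records whether each scheduled session was completed. A participant could complete every scheduled endurance session and still log at most 30% of the required minutes from those sessions.

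**Working it through.** The check multiplies sessions per week by minutes per session and compares the product with each stated weekly total.

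**Inputs.** Required time: 150 min/week (Section 7.1.3). Endurance sessions: 1 per week (Sections 7.1.1 and 7.1.3). Session length: 40 min in Months 9–12 and 45 min in Months 13–18 (Table 7). Programme: 3 sessions of 30–45 min (Section 7.1), or 3 hours in total (Section 7.1.1).

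**1. Endurance time against the requirement**

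| Period | Scheduled min/week | Share of 150 | Shortfall | Sessions needed for 150 |
|---|---|---|---|---|
| Months 9–12 | 1 × 40 = 40 | 40/150 = 26.7% | 110 min | 150/40 = 3.75 |
| Months 13–18 | 1 × 45 = 45 | 45/150 = 30.0% | 105 min | 150/45 = 3.33 |

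The stated 150 minutes is not reproduced from the schedule.

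**2. If 150 minutes counts all three weekly sessions**

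- All three at the Table 7 length: 3 × 40 = 120 min to 3 × 45 = 135 min.
- Endurance at the Table 7 length and the other two at 30–45 min: 40 + 2 × 30 = 100 min to 45 + 2 × 45 = 135 min.
- Using the Section 7.1.1 total: 3 × 60 = 180 min.

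The first two fall short of 150 and the third exceeds it. On this reading, whether the Month 9 aim is met depends on which programme total is used.

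**3. The two programme totals**

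- Section 7.1: 3 × 30 = 90 to 3 × 45 = 135 min/week.
- Section 7.1.1: 180 min/week.
- Gap: 180 − 135 = 45 to 180 − 90 = 90 min/week.

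With an endurance session of 40–45 min, a 180-minute week leaves 180 − 45 = 135 to 180 − 40 = 140 min for OEP and FAME together. Their average is 135/2 = 67.5 to 140/2 = 70 min. However the time is divided, at least one of the two must exceed the 45-minute upper limit in Section 7.1.

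**4. The 65% floor**

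Table 7 prescribes 50–60% of HRmax in Months 1–8 and first reaches 65% in Month 9. A floor applying from the start would contradict Table 7; a floor applying from Month 9 would not. The text gives no start month. A participant who halts progression at 60%, as the preceding sentence permits, would not meet the floor, and the text does not address that case.

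**The case against.** The strongest counter-argument is that the Month 9 aim refers to a recommendation for physical activity in general, so 150 minutes may mean all weekly activity. With the 3-hour total of Section 7.1.1, the aim would then be met. The aim sentence does allow this reading. It does not resolve the text, because Section 7.1 gives at most 135 minutes. The later requirement also ties the 150 minutes to 65% of HRmax, and Sections 7.1.1 and 7.1.2 give no heart-rate intensity for OEP or FAME. Minutes from those sessions are not expressly excluded; the protocol does not say what counts.

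Three other points have some force.

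- The session length in Section 7.1 sits next to a literature rationale and could be read as describing a class of programme. The sentence does say that it describes the intervention deployed in this project, so the conflict with 3 hours remains, though it is less clear-cut than the endurance conflict.
- Packages are tailored and participants choose their activity, so some variation in dose is intended, and extra sessions are not forbidden. That does not explain a fixed requirement more than three times the scheduled endurance time.
- The protocol does not define full adherence. Table 6 also lists a heart rate monitor and a calendar with diary for endurance training, and scoring may be set out in an analysis plan not seen here. The adherence consequence is therefore a risk, not an established flaw.

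**Conclusion.** The concern holds. From Month 9 the scheduled endurance session supplies 26.7–30.0% of the required weekly minutes, so the two instructions differ 3.33- to 3.75-fold. That figure assumes that the 150 minutes refers to endurance time and that only scheduled sessions count. If all physical training counts, the answer depends on two programme totals that differ by 45–90 minutes a week and fall on either side of 150. The missing start month for the 65% floor is a lesser ambiguity: a Month 9 start would be consistent with Table 7 but is not stated.

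This should be corrected. It affects the clarity of the prescription and the description of the dose delivered. It does not invalidate the comparison of the platform with no treatment.

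**What to change.** The sponsor should reconcile Sections 7.1, 7.1.1 and 7.1.3 and Table 7 into one schedule that gives, for each period, sessions per week, minutes per session, minutes per week and %HRmax. The text should also state:

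- whether the 150 minutes counts endurance training only or all physical activity;
- whether each element is required or recommended;
- from which month the 65% floor applies, and how it applies to participants who halt intensity increases.

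Endurance adherence, as recorded under Section 6.3 and Table 6, should then be measured against that schedule. The values are for the sponsor's exercise and medical leads to decide; none is proposed here.

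The cost is protocol wording and a matching platform and diary schedule. The stated weekly dose may have to be restated. Reconciling the text needs no extra staff or participants.
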